6.2.1.2 Overdose

The effects of overdose of this product are not known. The administered AMG 427 dose may be up to 10% lower or higher than specified in the protocol due to pump variation and will not be considered an overdose. A dose of up to 10% higher than the intended dose may not require specific intervention.

In any case of overdose, consultation with the Amgen medical monitor is strongly recommended for prompt reporting of clinically apparent or laboratory adverse events possibly related to overdosage. Consultation with the Amgen medical monitor is also strongly recommended even if there are no adverse events, in order to discuss further management of the subject. If the overdose results in clinically apparent or symptomatic adverse events, the subject should be followed carefully until all signs of toxicity are resolved and the adverse event(s) should be recorded/reported per Section [9.2.1.2](#).

A dose of > 10% higher than the intended AMG 427 dose will be considered clinically important and classified as a serious adverse event under the criterion of "other medically important serious event" per Section [9.2.1.2](#).

6.2.1.3 Dose-cohort Study Escalation and Stopping Rules, Dose Limiting Toxicities (DLTs)

A DLT will be defined as any of the events described below occurring in a subject during the DLT window. The DLT window will start on D1 (start of the administration of the first dose) and last for 28 days for all cohorts. Any adverse event occurring outside the DLT window that is determined by the investigator to be possibly related to the investigational product, which is seen more frequently or is more severe than expected or is persistent despite appropriate management, can be determined to be a DLT upon unanimous

recommendation by the DLRT after review of the adverse event and all available safety data.

DLT Evaluation

A subject will be DLT-evaluable if the subject has received the doses planned for the respective cohort, and completed the DLT window of 28 days for all cohorts. The DLT window may also be extended to assess events starting within the window in case the DLT definition is time dependent (eg, in case of neutropenia).

A subject is not DLT-evaluable if he/she drops out before completion of the DLT window for reasons other than a DLT; exception: if a subject has received the planned doses in cycle 1 and drops out within 1 week of the completion of the DLT period due to progressive disease, that subject will be considered DLT-evaluable and will not be replaced. All available safety data for subjects who are not DLT evaluable will still be evaluated and considered in DLRM recommendations. A DLT will be defined as any of the events described below occurring in a subject during the DLT window unless clearly attributable to causes other than AMG 427 treatment. The CTCAE version 4.0 (see [Appendix A](#)) will be used to assess toxicities/adverse events with the exception of CRS (see [Table 6](#) for grading criteria of CRS) and **immune-effector associated neurotoxicity syndrome (ICANS)** (see [Table 8](#) for grading criteria of ICANS).

Events to be considered as DLTs and exceptions are listed below:

- Cases of drug-induced liver injury confirmed by Hy's Law criteria
- Any treatment-related death
- Grade 2 or 3 CRS meeting any of the criteria listed below:
 - Grade 2 CRS that does not resolve, with or without intervention, to \leq grade 1 within 7 days will be considered a DLT
 - Grade 3 CRS that does not resolve, with or without intervention, to \leq grade 2 within 5 days, or \leq grade 1 within 7 days, will be considered a DLT
 - Grade 3 CRS reported at the initial run-in dose (ie, at MTD1; applicable only after MTD1 has been defined) will be considered a DLT
 - Two separate events of grade 3 CRS
- Grade 4 CRS/infusion reactions occurring during AMG 427 treatment, immediately stop the infusion. Permanently discontinue AMG 427 therapy.
- Grade 3–5 non-hematologic toxicity not clearly resulting from the underlying leukemia EXCEPT:
 - alopecia
 - grade 3 rash
 - grade 3 fatigue, asthenia, fever, anorexia, or constipation

- grade 3 nausea, vomiting or diarrhea not requiring tube feeding, total parenteral nutrition, or requiring or prolonging hospitalization
- infection, bleeding, or other expected direct complication of cytopenias due to active underlying leukemia
- grade 3 infusion reaction including CRS, if successfully managed and which resolves within 12 hours
- grade 3 TLS if it is successfully managed clinically and resolves within 7 days without end-organ damage.
- Grade 4 neutropenia that persists beyond 42 days in the absence of leukemia
- Laboratory parameters \geq grade 3, not considered clinically relevant, and improved to \leq grade 2 within 72 hours, will not be considered DLT's. Laboratory parameters with long half-lives, ie, ALT, GGT, ALP, and lipase, will likewise not be considered DLT's if they are not considered clinically relevant, and improve to grade \leq 2 within 7 days.
- Grade 3 transaminitis (per CTCAE criteria) reported for subjects with grade 2 CRS (per Lee et al, 2019 criteria) will not be reported as a DLT if there is improvement to CRS \leq grade 1 within 7 days.

The dosing schedule is described by a schema in [Figure 2](#).

See Section [3.1](#) for description of dose escalation and stopping rules and Section [3.4](#) for description of replacement of subjects.

Subjects who have experienced a DLT at a certain dose level may continue to receive AMG427 at a lower dose, if AMG 427 has shown a potential for benefit in the specified subject, the subject's adverse events have reduced to grade 2 or lower, and after discussion with the Amgen Medical Monitor.

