3.1.2.2 Maximum Tolerated Dose 2 (MTD2)

[figure not shown]
Dose escalation for the MTD2 following the initial dosing (MTD1) will proceed after MTD1 is determined and implements a dose step. The cohort for which a dose step will be implemented will start treatment for the first dose at the MTD1 assessed in the dose escalation for the first MTD. After this run-in dose, there may be a dose increase to the next higher dose as per the dosing schedule shown in [Table 3](#) of the protocol. If this treatment schedule is tolerated, the following dose cohorts will continue to receive the run in (initial) dose at MTD1 to assess the MTD2. The target (second) dose will be increased until an MTD2 is reached. Testing of an MTD3 will be guided in the same way by the BLRM and the DLRT review after considering all information.

Subjects who complete the DLT period (see [Section 6.2.1.4](#)) may proceed to a higher dose level for the following treatment cycle once the next dose cohort has been deemed safe by the DLRT, after consultation with the sponsor, if the subject has:

- No DLT reported during or after the completion of the DLT period

See [Section 7.2.2](#) for details on assessments applicable in case of intra-subject dose escalation. Dose limiting toxicities experienced by subjects after completing the DLT period will be considered in the BLRM design to account for any late onset toxicity.

Single Subject Cohorts

In the initial dose escalation cohorts, a single subject will be enrolled until any pharmacologic activity (including but not limited to infusion reaction, CRS, drop in white count) is noted. Evidence of pharmacologic activity will trigger multiple subject enrollment in the same and all subsequent cohorts. The initial dose levels are anticipated to be lower than the dose levels at which any clinical activity related to AMG 427 may be observed.

Multiple Subject Cohorts

Once multiple subject cohorts are triggered as described above, the same and subsequent cohorts will enroll 2 to 4 evaluable subjects based on BLRM output.

Time interval between Enrollment of Subjects in Each Cohort

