Hypotension	None	Not requiring vasopressors	Requiring a single vasopressor (not including vasopressin)	Requiring multiple vasopressors (not including vasopressin)
		And/or ^b		
Hypoxia	None	Requiring low-flow (≤ 6 L/minute) nasal cannula or blow-by	Requiring high-flow nasal cannula (> 6 L/min), facemask, non-rebreather mask, or Venturi mask	Requiring positive pressure (eg, CPAP, BiPAP, intubation and mechanical ventilation)

ASTCT = American Society for Transplantation and Cellular Therapy; BiPAP = bilevel positive airway pressure; CPAP = continuous positive airway pressure; CRS = cytokine release syndrome

Organ toxicities associated with CRS may be graded according to CTCAE v4.0 but they do not influence CRS grading.

^aFever is defined as temperature $\geq 38^{\circ}\text{C}$ not attributable to any other cause. In subjects who have CRS then receive antipyretic or anticytokine therapy such as tocilizumab or steroids, fever is no longer required to grade subsequent CRS severity. In this case, CRS grading is driven by hypotension and/or hypoxia.

^bCRS grade is determined by the more severe event: hypotension or hypoxia not attributable to any other cause. For example, a subject with temperature of 39.5°C , hypotension requiring 1 vasopressor, and hypoxia requiring low-flow nasal cannula is classified as grade 3 CRS.

Table 7. Management of Cytokine Release Syndrome

Description of CRS Severity ^a	Minimum Expected Intervention	Instructions for Interruption of AMG 427
Fever (temperature $\geq 38^{\circ}\text{C}$) without hypotension and hypoxia	
• Administer symptomatic treatment (eg, paracetamol/acetaminophen for fever).• Administer tocilizumab^b 4 to 8 mg/kg IV over 1 hour (not to exceed 800 mg). If no clinical improvement in signs and symptoms of CRS after the first dose, repeat tocilizumab every 8 hours (maximum of 3 doses in a 24-hour period; maximum total of 4 doses). If improving discontinue tocilizumab. Monitor for CRS symptoms including vital signs and pulse oximetry at least Q2 hours for 12 hours or until resolution, whichever is earlier. If symptoms of grade 1 CRS do not improve after 24 hours consider managing as grade 2.	

Page 1 of 4

Footnotes defined on next page of the table

Table 7. Management of Cytokine Release Syndrome

Description of CRS Severity ^a	Minimum Expected Intervention	Instructions for Interruption of AMG 427

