10.5.2 Primary Endpoint

Safety Endpoints

Unless otherwise specified, statistical analyses on safety endpoints will be done using subjects from the safety analysis set, which includes subjects that are enrolled and received at least 1 dose of AMG 427.

Subject incidence of DLTs will be used to fit the BLRM model to estimate the probability of having a DLT across dose levels.

Adverse Events

Subject incidence of all treatment-emergent **and treatment-related** adverse events will be tabulated by system organ class, preferred term, **and worst severity grade**. The number and percentage of subjects reporting adverse events will be evaluated overall and by dose level and will also be tabulated by relationship to study drug.

Tables of **treatment-emergent and treatment-related** fatal adverse events, serious adverse events, and adverse events leading to withdrawal from investigational product or other protocol-required therapies will also be provided.

Clinical Laboratory Tests

Clinical chemistry, hematology, and urinalysis data will be presented and reviewed for each subject. Values outside the normal laboratory reference ranges will be flagged as high or low on the listings. Depending on the size and scope of changes in laboratory

data, summaries of laboratory data over time and/or changes from baseline over time may be provided. Tables of maximum shifts from baseline for selected laboratory values may also be provided.

Vital Signs

Vital signs data will be presented and reviewed for each subject. Depending on the size and scope of changes, summaries of vital signs data over time and/or changes from baseline over time may be provided.

Electrocardiograms

Summaries over time and/or changes from baseline over time will be provided for all ECG parameters.

Subjects' maximum change from baseline in QT interval corrected by Fridericia's formula will be categorized and the number and percentage of subjects in each cohort will be summarized.

Subjects' maximum post baseline values will also be categorized and the number and percentage of subjects in each cohort will be summarized.

All on-study ECG data will be presented, and select parameters of interest may be plotted.

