#### **Safety Stopping Rules during Dose Expansion:**

During dose expansion, Amgen will conduct evaluations of the ongoing DLT event rate to assess if the threshold for pausing enrollment has been reached. If these stopping rules are met, then enrollment to the dose expansion will be paused pending a review of safety data and available pharmacokinetic, pharmacodynamics, and efficacy data by the DLRT. This review may result in early termination of the study, notification to Health Authorities, or may result in re-initiation of enrollment. The DLRT may implement additional measures, as appropriate, to reduce the risk of toxicity or to adapt and manage the toxicity. The stopping rules to pause enrollment use a Bayesian approach proposed by [Thall, et al \(1995\)](#); enrollment to dose expansion will be halted if the posterior probability that the DLT event rate is greater than 20% is > 80%. The stopping boundaries assuming a prior distribution of Beta (0.40, 1.60) are presented in [Table 1](#)

and the operating characteristics with pre-specified batch size of 6 new subjects per batch are presented in [Table 2](#). The evaluations could occur more frequently if necessary to address emerging safety concerns.

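### The DLT exemption for grade 3 transaminitis with grade 2 CRS tests recovery of CRS but not of ALT or AST, so on its face a persistent grade 3 elevation is not counted (minor; cheap to correct)

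*Protocol*

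**What the plan says.** Under Protocol 6.2.1.3, non-hematologic toxicity of grade 3 to 5 is a DLT unless an exception applies. Two bullets near the end of the list bear on liver enzymes.

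- **Laboratory bullet.** Laboratory values of grade 3 or higher are excused if they are not clinically relevant and fall to grade 2 or less within 72 hours. ALT, GGT, ALP and lipase get longer: they are excused "if they are not considered clinically relevant, and improve to grade" 2 or less within 7 days. AST is not named, so the 72-hour limit applies to it.
- **CRS bullet.** Grade 3 transaminitis with grade 2 CRS "will not be reported as a DLT if there is improvement to CRS" grade 1 or less within 7 days. No ALT or AST condition follows.

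The note under Protocol Table 6 (section 6.6) reads: "Organ toxicities associated with CRS may be graded according to CTCAE v4.0 but they do not influence CRS grading".

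On use of the count, Protocol 10.5.2 says: "Subject incidence of DLTs will be used to fit the BLRM model to estimate the probability of having a DLT across dose levels". SAP 3.3 says that "enrollment to dose expansion will be halted if the posterior probability that the DLT event rate is greater than 20" percent is above 80%. The DLT definition in SAP section 5 refers back to Protocol 6.2.1.3 and adds no liver condition.

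**The concern.** The exemption excuses one toxicity on evidence about another. CRS is graded on fever, hypotension and hypoxia. A subject can be back at CRS grade 1 or less on day 5 with ALT still at grade 3 on day 20, and the CRS bullet is met. The laboratory bullet would not excuse that ALT value, but both bullets are written as separate exemptions with no order of precedence. Investigators flag DLTs on the Events CRF (SAP section 5), so the same event could be classified differently at different sites.

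DLTs are part of the primary endpoint, the BLRM input and the trigger for the expansion pause. An uncounted event biases the estimated DLT rate downward in the first two uses and makes a pause less likely in the third. Amendment 7 moved the pause rule from grade 4 and above adverse events to DLTs, so the definition now carries more weight than before.

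**Working it through.** **Step 1. What falls in the gap.** Setting the bullets and Table 6 side by side:

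| Event in the DLT window | Excused by the CRS bullet? |
|---|---|
| Grade 3 ALT/AST, grade 2 CRS settled by day 7, enzymes recovered by day 7 | Yes, as intended |
| Same, but enzymes still grade 3 after day 7 | Yes on its face; the laboratory bullet would not excuse it |
| Grade 2 CRS not at grade 1 or less within 7 days | No; the CRS itself is a DLT |
| Confirmed Hy's Law case | No; separately listed as a DLT |
| Grade 4 ALT/AST | No; the bullet covers grade 3 only |
| Grade 3 ALT/AST without grade 2 CRS | No; the laboratory bullet applies |

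Only the second row is at issue. The argument from Table 6 applies to cohorts graded on the 2019 CRS scale (SAP 9.6.2), which is the scale the bullet cites.

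**Step 2. Reproduce the pause rule.** Inputs from Protocol 10.3 and SAP 3.3: prior Beta(0.40, 1.60), looks every 6 subjects, pause if Pr(p > 0.20) > 0.80. The boundary at n subjects is the smallest r with Pr(p > 0.20 | Beta(0.4 + r, 1.6 + n − r)) > 0.80.

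| n | one below the boundary | at the boundary |
|---|---|---|
| 6 | 2: 0.707 | 3: 0.914 |
| 12 | 3: 0.608 | 4: 0.821 |
| 18 | 5: 0.747 | 6: 0.883 |
| 24 | 6: 0.688 | 7: 0.831 |
| 30 | 8: 0.783 | 9: 0.885 |
| 36 | 9: 0.740 | 10: 0.848 |
| 42 | 10: 0.700 | 11: 0.812 |
| 48 | 12: 0.778 | 13: 0.865 |

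All eight boundaries in Protocol Table 26 (SAP Table 1) agree. An exact binomial recursion over these looks, with maximum N of 40 (R/R) and 50 (MRD+), gives at a true rate of 0.30 a pause probability of 78.9% and mean N of 19.9, and 85.5% and 21.6. These match Protocol Table 27. The printed figures are right for whatever is counted; the question is what is counted.

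**Step 3. Illustrate an undercount.** Let f be the share of DLT subjects whose only DLT is an exempted event. The documents do not give f; it is assumed. The counted rate is 0.30 × (1 − f).

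| f | counted rate | all subjects affected | pause, R/R | pause, MRD+ |
|---|---|---|---|---|
| 0% | 0.300 | 0% | 78.9% | 85.5% |
| 5% | 0.285 | 1.5% | 73.4% | 80.5% |
| 10% | 0.270 | 3.0% | 67.2% | 74.4% |

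**Step 4. Scale check on f.** Protocol 2.2.4 lists grade 3 or higher ALT increase in 2 subjects: 2/53 = 3.8% of those treated, or 5.9% as printed (which corresponds to 2/34). Neither duration nor accompanying CRS grade is given, and doses were mixed. At f = 10%, 3% of all subjects would be exempt cases, so nearly all such events would have to be grade 3, persistent, paired with grade 2 CRS that settled, and not otherwise a DLT. That makes 10% an upper case.

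The effect on the BLRM was not computed because the dose levels are redacted. The direction is the same: fewer counted DLTs lower the estimated toxicity.

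**The case against.** The strongest reply is that the event is not lost. Protocol 10.4.2 and SAP 7.1 require the DLRT to review every grade 3 or higher toxicity that misses the DLT criteria. In expansion it meets at every sixth subject, the same batch size as the pause rule. Crossing the boundary only pauses enrollment pending review by that same team, and the BLRM recommendation is a ceiling that the DLRT may go below. The event also appears in the treatment-emergent and treatment-related adverse event tables, which are part of the primary endpoint. This stands, and it is the main reason the point is minor. It does not close the gap: the DLRT may, but need not, give such an event weight, and review does not put it in the DLT count.

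Two further routes help less. An event outside the DLT window that "is persistent despite appropriate management, can be determined to be a DLT upon unanimous" recommendation of the DLRT can be added, and "Dose limiting toxicities experienced by subjects after completing the DLT period will be considered in the BLRM design". The first needs unanimity and is written for events outside the window; the second applies only once something has been called a DLT. "Cases of drug-induced liver injury confirmed by" Hy's Law remain DLTs, but isolated persistent grade 3 ALT/AST is not such a case.

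It can also be argued that the bullet deliberately treats transaminitis during moderate CRS as part of the CRS event. That is a reasonable aim, and transient elevations should stay exempt. It does not explain why persistence should be ignored when the neighbouring bullet takes it into account.

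A reader might infer that subjects with persistent liver injury would go on being dosed. The documents do not support that: Protocol 6.2.1.4 governs restart after adverse events, and 6.4.1 and 6.4.2 govern withholding for hepatotoxicity. A reader might also take the DLT described in the Amendment 5 rationale as an exempted case. It was grade 3 CRS with grade 4 ALT, so it falls outside the bullet and was counted.

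**Conclusion.** The point holds, at minor severity. The CRS bullet's recovery test does not measure the toxicity it excuses, and on its face persistent grade 3 ALT/AST is not a DLT. It would be too strong to say the exemption certainly applies, because precedence over the laboratory bullet is not stated. The defect is therefore a gap on one reading and an ambiguity on the other.

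The consequence is limited to the DLT count and the decisions built on it. Under the assumed 5% share at a true rate of 0.30, the pause probability drops by 5.5 percentage points in R/R AML (78.9 − 73.4) and 5.0 in MRD+ AML (85.5 − 80.5). At a true rate of 0.40 the same share moves the R/R figure only from 97.4% to 95.8%. A reader might infer that the pause rule is materially weakened; the documents do not show that. A 20% share, for example, would mean 6% of all subjects (0.20 × 0.30), more than the 3.8% or 5.9% with grade 3 or higher ALT increase of any kind.

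**What to change.** Reword the CRS bullet along these lines:

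*Grade 3 ALT or AST in a subject with grade 2 CRS is not a DLT provided that CRS is at grade 1 or less within 7 days, ALT and AST are both at grade 2 or less within 7 days of first reaching grade 3, and the elevation is not judged clinically relevant apart from the CRS. Grade 3 ALT or AST that does not meet these conditions is a DLT.*

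The last sentence settles precedence. Keeping the clinical-relevance condition avoids loosening the rule for anyone who now reads the two bullets together. State that 7 days for AST deliberately extends the laboratory bullet's ALT limit, for CRS-associated cases only; elsewhere AST stays under the 72-hour rule.

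The final MTD estimate pools all DLT-evaluable subjects from escalation and expansion (Protocol 3.1.3). It should therefore use one definition throughout, at least in a sensitivity run of the BLRM that counts any previously exempted persistent event as a DLT. This gives a listing of past exempted events a defined purpose.

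Cost: one protocol bullet, one listing and one sentence in SAP 9.6.1 for the sensitivity run. The SAP's DLT definition needs no rewording because it refers to the protocol. The downside is possibly a few more counted DLTs.

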6.2.1.4 Dosage Adjustments, Delays, Rules for Withholding or Restarting, Permanent Discontinuation

Treatment Interruption

Significant events attributed to the drug or infusion may require treatment interruption.

Note: The definition of treatment interruption may include interruption of infusion or delay of the subsequent dose.

Events leading to treatment interruption may include:

- The subject experiences a grade \geq 3 adverse event related to the infusion/drug
- Technical problem with the syringe/infusion pump/syringe pump
- The investigational product is incorrectly prepared or administered (eg, overdose)

Treatment Interruption and Re-Start in Case of Adverse Events During the Infusion

Treatment must be modified for any clinically relevant (as determined by investigator) adverse events that occur during the infusion and are related to investigational product, as follows:

- grade 2 adverse event: **Prior to next dose, adverse event must resolve to grade 1 or less for at least 24 hours, including isolated lab abnormalities and organ toxicity labs**
- grade 3 adverse event: Interrupt the infusion until the adverse event is grade ≤ 1 **for at least 24 hours prior to the next dose of AMG 427**. Restart at the same dose if interruption is ≤ 72 hours. If interruption is > 72 hours, restart at a lower dose (last safe dose as **recommended** by DLRT or a lower dose). If the adverse event is a DLT, follow Section 6.2.1.3 for management of DLT.
 - **Subjects who experience CRS grade 3 should have next dose delayed until CRS resolves to grade ≤ 1 for at least 24 hours prior to the next dose of AMG 427 (including isolated lab abnormalities and organ toxicity labs, except for liver function tests, which must resolve to grade 2 or less), and should have next dose(s) reduced by one-half or more, if given on scheduled day (please consult with the study medical monitor).**
- grade 4 adverse events during the infusion: Permanently discontinue the investigational product

The Amgen medical monitor has to be consulted prior to a planned re-start.

In case of a dose reduction, re-escalation to the target dose can be considered for the next infusion if treatment at the lower dose has been well tolerated. An intermediate dose level may be administered prior to stepping up to the target dose after consultation with the Amgen medical monitor.

The subject should be hospitalized for at least 72 hours after re-start of the infusion.

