If possible, the number of infusions at the target dose in a cycle should sum up to the planned number of infusions. In this case, the cycle would still be DLT-evaluable.

Permanent Discontinuation

A subject will permanently discontinue treatment with investigational product in the event of:

- dose-limiting or other unmanageable toxicity
 - except subjects who have experienced a DLT at a certain dose level may continue to receive AMG427 at a lower dose, if AMG 427 has shown efficacy in the specified subject, and the subject's adverse events have reduced to grade 2 or lower, and after discussion with the Amgen Medical Monitor.
- grade 4 CRS
- grade 2 or 3 CRS meeting any of the criteria listed below:

- grade 2 or 3 CRS that does not improve to \leq grade 1 within 7 days
- grade 3 CRS that does not improve to \leq grade 2 within 5 days
- grade 3 CRS at the initial run-in dose for a cycle (ie, at the MTD1) (for cohorts with dose step only)
- If a subject experiences 2 separate grade 3 CRS events
- disease progression as defined by revised IWG response criteria ([Appendix E](#))
- withdrawal of subject's consent to treatment
- subject or investigator not compliant with the study protocol
- occurrence or progression of a medical condition, which in the opinion of the investigator, should preclude further participation of the subject in the study
- a treatment interruption of more than 21 days due to an adverse event not clearly related to the underlying disease (except neutropenia)
- occurrence of a CNS-related adverse event considered related to AMG 427 by the investigator and meeting 1 or more of the following criteria:
 - more than 1 seizure
 - a CNS-related adverse event grade 4
 - a CNS-related adverse event leading to treatment interruption that needed more than 1 week to resolve to grade \leq 1
- graft-versus-host disease
- investigator's decision that a change of therapy (including immediate HSCT) is in the subject's best interest

Females who become pregnant while on study through 4 weeks after receiving the last dose of study drug will not receive subsequent scheduled doses and will be followed for safety until the end of study visit.

Males on study through 4 weeks after receiving the last dose of study drug must practice sexual abstinence or use a condom while on study through 4 weeks after receiving the last dose of study drug.

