
 • Fever (temperature $\geq 38^{\circ}\text{C}$) with: • Hypotension requiring multiple vasopressors (excluding vasopressin) AND/OR • Hypoxia requiring positive pressure (eg, CPAP, BiPAP, intubation and mechanical ventilation) 	
Admit to ICU for close clinical and vital sign monitoring per institutional guidelines.
 
 • Tocilizumab^b 8 mg/kg IV over 1 hour (not to exceed 800 mg). If no clinical improvement in signs and symptoms of CRS after the first dose, repeat tocilizumab every 8 hours (maximum 3 doses in a 24-hour period). If improving discontinue tocilizumab. 
Administer methylprednisolone up to 1000 mg once per day for 3 days. If improving manage as appropriate grade above and continue corticosteroids until severity is grade 1 or less then taper as clinically appropriate.
 
If not improving consider methyl prednisolone 1000 mg two to three times a day or alternate therapy.
	
Immediately stop the infusion and permanently discontinue AMG 427 therapy.

Page 4 of 4

BiPAP = bilevel positive airway pressure; CPAP = continuous positive airway pressure; CRS = Cytokine Release Syndrome; ICU = intensive care unit;

IL-6 = interleukin 6; IL-6R = interleukin 6 receptor; IV = Intravenous; LFT(s) = liver function test(s); MTD = maximum-tolerated dose

^a Grading system for CRS (Lee et al, 2019)

^b If tocilizumab is not available, another IL-6/IL-6R inhibitor eg, siltuximab may be used per institutional practice for CRS.

Re-start of treatment after CRS:

Please refer to the general guidance for re-start of treatment after adverse events in Section [6.2.1.4](#)

For grade 3 and 4 CRS, please see Section [6.2.1.3](#) for DLT considerations.

Immune-effector Cell-associated Neurotoxicity Syndrome (ICANS):

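### Section 6.2.1.3 allows lower-dose treatment after any DLT without saying that the permanent-discontinuation rules come first, and its benefit test differs from that in 6.2.1.4

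*Protocol*

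**What the plan says.** **The permission.** The closing paragraph of protocol Section 6.2.1.3 says that subjects with a DLT may go on "at a lower dose, if AMG 427 has shown a potential for benefit in the specified" subject. The two further conditions are recovery of adverse events to grade 2 or lower and discussion with the medical monitor. The paragraph is not limited to particular DLTs and does not refer to Section 6.2.1.4, Table 7 or Section 6.4.1.

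**The stops.** Section 6.2.1.4, under Permanent Discontinuation, is mandatory. Its first bullet, on dose-limiting or unmanageable toxicity, carries the same exception, but with the condition "if AMG 427 has shown efficacy in the specified subject". The CRS and CNS stops are separate bullets with no exception, for example "If a subject experiences 2 separate grade 3 CRS events" and "a CNS-related adverse event grade 4". Table 7 repeats most of the CRS stops. Section 6.4.1 calls for permanent discontinuation for defined liver injury, and 6.4.3 bars rechallenge where those criteria are clearly met.

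**The cross-references.** For grade 3 events during the infusion, 6.2.1.4 says: "If the adverse event is a DLT, follow Section 6.2.1.3 for management of DLT". Section 6.6 points the other way for restart after CRS: "Please refer to the general guidance for re-start of treatment after adverse events in Section" 6.2.1.4. The synopsis allows further cycles only while the 6.2.1.4 criteria are not met. Sections 3.5.1 and 6.2.1.1 give the cycle limit without that condition.

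**The concern.** The same event can fall under a permission in one section and a mandatory stop in another. A site that follows the pointer to 6.2.1.3 for a grade 3 DLT reads three conditions for continuing and no reminder of the stops. A subject with two grade 3 CRS events that have both resolved meets the recovery condition there, but must stop under 6.2.1.4.

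The two sections also set different benefit standards for one decision. A subject whose blasts are falling but who has no response could arguably pass the first test and fail the second.

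What is at stake is consistent conduct and subject safety. Sites and sponsor could apply different rules, and a subject who should stop could be treated again. CRS was reported in 42 of 53 subjects and was serious in 8 (Section 2.2.4), and Table 1 records a fatal event, so these rules should leave no room for doubt.

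**Working it through.** No arithmetic applies beyond counting, so the check sets the texts side by side.

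**Step 1. Match the grade 2 and 3 CRS DLT criteria in 6.2.1.3 to stops that carry no exception.**

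| DLT criterion | Separate stop in 6.2.1.4 | Repeated in Table 7 |
|---|---|---|
| Grade 2 CRS not at grade 1 or less in 7 days | yes | yes |
| Grade 3 CRS missing the 5-day or 7-day limit | yes | yes |
| Grade 3 CRS at the run-in dose (MTD1) | yes | yes |
| Two separate grade 3 CRS events | yes | no |

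Result: four of four are stops in 6.2.1.4, and three of the four are repeated in Table 7.

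**Step 2. Set aside grade 4 CRS and infusion reactions.** Section 6.2.1.3 itself says to discontinue permanently for these, so they are not counted as a conflict.

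**Step 3. Liver injury.** Hy's Law injury is a DLT in 6.2.1.3, which does not define it. Section 6.4.1 requires all of its criteria together: raised AST or ALT, bilirubin or INR above limits, ALP no more than 2 x ULN and no other apparent cause. It gives an AST/ALT threshold only for a baseline below ULN, whereas inclusion criterion 107 admits values up to 3 x ULN. An overlap is likely, but an exact match cannot be shown.

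**Step 4. Other overlaps.** A DLT also includes grade 3–5 "non-hematologic toxicity not clearly resulting from the underlying leukemia", with listed exceptions. A related grade 4 CNS event, or more than one seizure, can therefore be a DLT and a 6.2.1.4 stop at once; Table 8 grades an ICANS seizure as at least grade 3. These are examples, not a full count.

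**Step 5. Do the conditions in 6.2.1.3 screen these cases out?** No. Resolved grade 3 events pass the recovery condition. So, literally, does CRS that stays at grade 2, although its failure to resolve is what made it a DLT. The next-dose rules in 6.2.1.4 and Table 7, which require grade 1 or less for at least 24 hours, delay a dose but do not end treatment.

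**Step 6. Compare the two versions of the exception.** Recovery grade: same. Medical monitor discussion: same. Benefit: different. One condition of three differs.

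**The case against.** The strongest reply is that the protocol already settles the order. The 6.2.1.4 list is mandatory, and its exception is indented under the first bullet only. A permission elsewhere does not cancel a mandatory stop. The synopsis, Table 7, the restart reference in Section 6.6 and the bar in 6.4.3 all point the same way. The Section 6.6 reference to 6.2.1.3 for DLT considerations may mean only whether the event counts as a DLT. Most of this stands: 6.2.1.4 is very probably meant to govern. What it leaves is that 6.2.1.3 does not say so, that 6.2.1.4 itself sends one class of DLT there for management, and that the two benefit tests differ whichever section governs.

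A reader might infer more than the documents support:

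- **That the protocol authorises re-dosing after a mandatory stop.** The texts just listed argue against that. The defect is an unstated order of precedence.
- **That re-dosing could be unsupervised.** Both versions require discussion with the medical monitor. The monitor, however, works from the same two texts.
- **That grade 4 events during the infusion are part of the conflict.** Section 6.2.1.4 stops them outright ("grade 4 adverse events during the infusion: Permanently discontinue the investigational product"). The pointer to 6.2.1.3 sits under grade 3 events only.
- **That Hy's Law is a fifth exact match.** Step 3 of the check shows why it is only likely.
- **That the missing limit in 3.5.1 and 6.2.1.1 suspends 6.2.1.4.** Those sections give a maximum number of cycles; silence there lifts nothing.

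**Conclusion.** The point holds as a conflict of wording on a safety rule. Four grade 2 or 3 CRS DLT criteria fall under the 6.2.1.3 permission although they are stops without exception in 6.2.1.4, three of them also in Table 7. A Hy's Law DLT is a likely further case. One of the three conditions for continuing differs between the two sections.

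This rests on reading the 6.2.1.3 paragraph as covering all DLTs, which is how it is worded, and on reading the 6.2.1.4 exception as attached to its first bullet only. The number of subjects affected cannot be derived from the documents. The DLT definition that the SAP takes from 6.2.1.3 is unchanged, as are the DLT counts, the sample size and the operating characteristics. It should be fixed because the correction is short and the risk includes a fatal event.

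**What to change.** In 6.2.1.3, and in the exception in 6.2.1.4, use one identical sentence to this effect: after a DLT, treatment at a lower dose is allowed only if no other permanent-discontinuation criterion in 6.2.1.4, Table 7 or 6.4.1 is met, the benefit test is met, adverse events have recovered to grade 2 or lower, and the medical monitor has been consulted. The recovery grade can stay as it is, with a note that the next-dose rules in 6.2.1.4 still apply.

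The sponsor should choose the benefit test, because this is a clinical trade-off. Section 6.6 places the higher CRS risk in the first few days after the initial dose and after a dose step, while Table 25 puts marrow assessment at D14 or D28. Requiring shown efficacy could therefore exclude many early DLTs that occur before any response has been assessed. A test of potential benefit keeps them eligible, but should say what evidence counts.

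Sections 3.5.1 and 6.2.1.1 could carry a cross-reference to 6.2.1.4, as the synopsis does. It would also help to say there whether a subject with a cycle 1 DLT who meets the exception may have further cycles.

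The cost is amendment wording. DLT definitions, data collection and analyses do not change. The downside is that subjects who meet a listed stop can no longer be re-treated under the 6.2.1.3 wording. If shown efficacy is chosen, the loss would be wider, and its size cannot be estimated from the documents.
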